## 8.1 Population Characteristics

### 8.1.1 Demographics

Demographic characteristics to be recorded at screening will include age, sex, race and ethnicity, and blood type. Employment will also be recorded at Baseline (Day 1).

### 8.1.2 Medical and Surgical History

Medical history findings (i.e. previous diagnoses, diseases, surgeries, and substance usage) meeting all criteria listed below will be collected at screening:

- Not pertaining to study indication
- Start before signing of informed consent
- Considered relevant to the study
- Include any information on cardiovascular risk, hepatic disease, renal impairment, prior use of PEGylated medications (e.g. PEG- interferon, PEG-anti-TNF), and concomitant medications

### 8.1.3 Disease History

Specific information on history of hemophilia to be recorded at screening will include date of diagnosis, start of therapy, start of prophylaxis, for all prior and current FVIII products within 12 months, estimated number of EDs, type of FVIII gene mutation (from history, if available), family history, FVIII level and type of assay, family and personal history of past inhibitor formation (including date of inhibitor testing, whether immune tolerance induction was performed, and recovery and half-life data, if available; [Section 1.3](#)), previous or current SHL treatment product and regimen, used for score calculation, within 12 months of Baseline Visit, and number and type of bleeds derived from the before-mentioned SHL time period of a minimum of 6 months within the last 12 months of study screening . If available, data on prior PK with the participants' previous SHL FVIII product (used for score calculation) will be collected (concentration timepoints, and half-life).

Blood samples will be collected at screening to determine the participant's vWF antigen levels, if not already available in the medical records. If available in the medical records, vWF antigen testing should have been performed within 12 months prior to enrollment.

### 8.1.4 Other

At screening, blood type will be recorded and BMI will be calculated.

Physical activity levels (medium/high [contact sports]; low [non-contact sports]; and sedentary) will be recorded at Baseline (Day 1).

## 8.2 Effectiveness Assessments

This is an exploratory study of the effect of using a risk score approach to select the most appropriate prophylaxis regimen for favorable clinical outcomes and reduced treatment burden. Planned time points for all effectiveness assessments are provided in the SoA ([Section 1.3](#)). Effectiveness variables to be evaluated are listed below (further details will be provided in the Statistical Analysis Plan [SAP]).

- ABR (total, joint, spontaneous)
- Jivi treatment frequency, expressed as total number of infusions per month

- Occurrence of participants with 0 and  $\leq$  1 spontaneous bleeds
- Quality of life, as measured by Haem-A-QoL or Haemo-QoL, PGI-C, EQ-5D-5L, TSQM, and WPAI
- Number and location of affected target joints, defined per ISTH

The primary effectiveness variables used in the determination of favorable outcome will be change in total ABR and FVIII treatment frequency (infusions/month). The primary endpoint is the occurrence of favorable outcome (see [Section 9.4.2](#) for additional details), defined as:

- no change of the risk score-assigned dosing regimen during the study, with one of the following:
  - improved ABR versus pre-study ABR and decreased frequency of administration versus pre-study frequency.
  - improved ABR versus pre-study ABR with similar frequency of administration versus pre-study frequency.
  - decreased frequency of administration versus pre-study frequency and similar ABR versus pre-study ABR.

**NOTE:** The full definitions of pre-study ABR, treatment frequency, and stable SHL prophylaxis are provided in [Section 9.4.2](#) and [Section 11.10](#).

### 8.2.1 Treatment Logs/Bleeding Verification

Treatment logs are commonly used for hemophilia participants for documentation of their home treatment. Home treatment and bleeding information are the key variables for evaluation of effectiveness. Study-specific treatment logs will be provided in the national language. The system for this study will be an eDiary since this allows for an interactive, record-stamp date and time of fulfillment and facilitates the clarification of data with the site as well as the data cleaning process. Participants will be provided access to the eDiary for the entire study. At the Baseline Visit, participants (and their parent[s] or legal guardian) will be trained in the use of the eDiary. These logs will be used to document the treatment data and bleeding episodes by the participants, and the data will be verified for accuracy and completion by the investigator or delegate during regularly scheduled interactions with the participant. Thus, the eDiary will be considered the source for these data. In the event a participant does not have internet access, alternative means of diary completion will be provided.

For each infusion of Jivi, information must be recorded in the diary as follows:

#### **Each infusion of Jivi:**

- a. Date and time
- b. Infusion record
- c. Individual vial/batch number (bar code scan from vial label or manual entry) and units administered
- d. Reason for treatment
  - Prophylaxis
  - Spontaneous bleed first treatment

- Trauma bleed first treatment
- Follow-up treatment
- Unscheduled Prophylaxis due to surgery
- Unscheduled Prophylaxis due to injury
- Unscheduled Prophylaxis due to activity
- Other (as specified by participant or legally authorized representative)

Infusions of Jivi as part of protocol-mandated visits and procedures will be recorded on the respective CRF pages.

All bleeding episodes (regardless if treated or not, or treated at home or under medical supervision) as well as any potential treatment with other hemophilia drugs will be recorded in the diary:

#### **Bleeding episode (onset)**

- a. Date and time of onset
- b. Type of bleed (spontaneous, trauma; joint, muscle, skin/mucosal, internal, other)
- c. Location
- d. Intensity (mild, moderate, severe)
- e. Treated [YES/NO]; If YES, the following is to be recorded:
  - Date and time
  - Number of infusions
  - Dose/infusion

#### **8.2.2 Patient Reported Outcomes**

The PRO data on QoL and health status, work and school productivity, pain, and treatment satisfaction will be collected. The objective of PRO data is to collect the participant's perspectives and opinions on the impact and effectiveness of Jivi in the treatment of hemophilia. Questionnaires will be filled out by the participant in the treatment center at Baseline (Day 1; Haem-A-QoL or Haemo-QoL, PGI-C, EQ-5D-5L, TSQM, and WPAI), Month 3 (EQ-5D-5L only), and Month 6 (EOS; Haem-A-QoL or Haemo-QoL, PGI-C, EQ-5D-5L, TSQM, and WPAI). [Appendix 2](#) provides representative examples of the PROs to be used in the study.

The following PROs assessments will be obtained:

- **Haemophilia specific quality of life (Haem-A-QoL and Haemo-QoL) questionnaires:**

The questionnaire will be used to capture the full impact of Jivi and the treatment modalities on the participants' hemophilia-specific QoL during the previous 4 weeks. The Haem-A-QoL is a hemophilia-specific QoL questionnaire for adults aged 18 years and above. The questionnaire has 41-items covering 6 domains: Physical Functioning, Role Functioning, Worry, Consequences of Bleeding, Emotional Impact, and Treatment Concerns. For participants 17 years and younger, the Haemo-QoL Short Form Questionnaire for children and adolescents will be used. The Haemo-QoL

Short Form contains 35 questions covering 9 domains: Physical Health, View of Yourself, Family, Friends, Others, Sports, Dealing, and Treatment.

The respondent burden for both questionnaires is approximately 15 minutes.

- **Patient's Global Impression of Change (PGI-C)**

The self-report measure PGI-C reflects a participant's belief about the efficacy of treatment. The PGI-C consists of a 7-point scale depicting a participant's rating of overall improvement. Participants rate their change as "very much improved," "much improved," "minimally improved," "no change," "minimally worse," "much worse," or "very much worse."

The respondent burden for the questionnaire is approximately 5 minutes.

- **Five-Level European Quality of Life Five Dimension (EQ-5D-5L)**

The EQ-5D-5L is a standardized health-related QoL questionnaire that provides a simple, generic measure of health for clinical and economic appraisal. The EQ-5D-5L descriptive system comprises 5 dimensions: mobility, self-care, usual activities, pain and discomfort, and anxiety and depression. Each dimension has 3 levels: no problems, some problems, or severe problems. The respondent is asked to indicate his/her health state by ticking (or placing a cross) in the box against the most appropriate statement in each of the 5 dimensions.

The respondent burden for the questionnaire is approximately 5 minutes.

- **Treatment Satisfaction Questionnaire for Medication (TSQM)**

The TSQM comprises 9 items across 3 domains focusing on effectiveness (3 items), convenience (3 items), and global satisfaction (3 items) of the medication over the previous 2 to 3 weeks, or since last use. All items have 5 or 7 responses, scored from one (least satisfied) to 5 or 7 (most satisfied). Item scores are summed to give 3 domain scores, which are in turn transformed to a scale of 0-100.

The respondent burden for the questionnaire is approximately 5 minutes.

- **Work Productivity and Activity Impairment (WPAI) questionnaire:**

The WPAI is a validated instrument to assess the effect of hemophilia on ability to work, attend classes, and perform regular daily activities in ages 12 and above. The WPAI will also contain classroom impairment questions. The questionnaire is self-administered and comprises 9 questions that elicit information on work, classroom, and daily activity impairment during the previous 7 days. Scores are expressed as percentages of impairment/productivity loss, with higher scores indicating greater impairment.

The respondent burden for this questionnaire is approximately 10 minutes.

### **8.2.3 Joint Status Assessment**

A joint status assessment (including target joints) will be recorded at baseline and EOS using the ISTH criteria. A target joint is defined as one having 3 or more spontaneous bleeds into a single joint within a consecutive 6-month period. Where there have been  $\leq 2$  bleeds into the joint within a consecutive 12-month period the joint is no longer considered a target joint (Blanchette et al., 2014).

## 8.3 Safety Assessments

Safety will be assessed by monitoring and recording all AEs, AEs of special interest (AESIs), and SAEs, and any abnormal findings observed during the performance of physical examinations.

Planned time points for all safety assessments are provided in the SoA ([Section 1.3](#)).

### 8.3.1 Measurements of Immunogenicity

All participants will be tested for inhibitors to FVIII according to the Bethesda assay as per local clinical practice. A positive inhibitor test is defined with a threshold of  $\geq 0.6$  BU/mL. Repeat testing should be obtained within 1 to 2 weeks of initial identification of a positive result. Only after confirmation of a second positive result does the inhibitor have to be reported as a SAE.

A low post-infusion FVIII level in the absence of detectable FVIII inhibitors indicates that loss of drug effect is likely due to anti-PEG antibodies. Jivi should be discontinued and participants switched to a previously effective FVIII product (refer to [Section 8.4.7](#) as this qualifies for an AESI-Loss of Efficacy [LoE]).

### 8.3.2 Physical Examinations

- Physical examinations will be performed at Baseline (Day 1) and EOS/Early Withdrawal Visit.
- A physical examination will include, at a minimum, assessments of the general health status, and review of systems. Height and weight will also be measured using a calibrated stadiometer (appropriate for the participant's age) and recorded.
- Investigators should pay special attention to clinical signs related to previous serious illnesses. Any abnormal finding should be documented.

### 8.3.3 Clinical Safety Laboratory Assessments

- See [Section 11.3](#) for the list of clinical laboratory tests to be performed and the SoA for the timing and frequency.
- The investigator must review the laboratory report, document this review, and record any clinically relevant changes occurring during the study in the AE section of the CRF. The laboratory reports must be filed with the source documents.
- Clinically significant abnormal laboratory findings are those which are not associated with the underlying disease, unless judged by the investigator to be more severe than expected for the participant's condition.

### 8.3.4 von Willebrand Factor (vWF) Antigen

The investigator must ensure absence of the following conditions or other factors which may influence the levels of vWF before drawing blood for the vWF test.

A number of transient clinical conditions can raise the vWF levels of individuals with congenital deficiency into the normal range. The vWF is an acute phase reactant and levels can increase due to stress, inflammation, acute infection, physical exercise, and following surgery. Levels can also increase with estrogen administration for contraception or hormone replacement ([Adcock et al., 2006](#)). Furthermore, two- to three-fold increases in the second and third trimesters of pregnancy have been observed ([Brandt, 2002](#); [Rick, 2002](#)). In addition,

vWF levels may increase during menstruation and should not be measured during active menstruation ([Brown et al., 2019](#)).

Note: Individuals with blood type O tend to have approximately 30% lower vWF levels than those with other blood types.

### **8.3.5      Pregnancy Testing**

A negative serum pregnancy test during screening and at Visit 5 (Month 3) and Visit 6 (Month 6) is required for women of childbearing potential (WOCBP) (see [Section 1.3](#)). If Visit 2 (baseline) occurs > 14 days after a female participant's last menstrual period, an additional pregnancy test is required. Premenarchal women, postmenopausal women with no menses for at least 1 year, or surgically sterilized women will not be required to undergo a pregnancy test. Confirmation of childbearing status should be documented in the medical history page of the CRF.

## **8.4          Adverse Events (AEs), Serious Adverse Events (SAEs), and Other Safety Reporting**

The definitions of an AE or SAE can be found in [Section 11.4](#).

The AEs will be reported by the participant (or, when appropriate, by a caregiver, surrogate, or the participant's legally authorized representative or HCP not involved in the study).

The investigator and any qualified designees are responsible for detecting, documenting, and recording events that meet the definition of an AE, AESI, or SAE. They remain responsible for following up on SAEs or AEs considered related to the study intervention or study procedures, or those events that caused the participant to discontinue the study.

Events of Special Interest have to be followed up regardless of causality or relationship to study intervention (see [Section 8.4.7](#)).

### **8.4.1       Time Period and Frequency for Collecting AE and SAE Information**

All AEs, AESIs, and SAEs will be collected from Baseline until the end of the Safety Follow-up Visit at the time points specified in the SoA ([Section 1.3](#)).

(S)AEs which are related to protocol-required study procedures (e.g. [S]AEs related to invasive study procedures) will be recorded as (S)AEs from the signing of the ICF until the start of study intervention. Medical occurrences that begin before the start of study intervention but after obtaining informed consent (and assent) but are diagnosed at screening or during the screening period (e.g. abnormal lab values) will be recorded on the Medical History/Current Medical Conditions section of the electronic CRF not the AE section, with the exception of bleeds occurring during the screening period which should be recorded in the patient's medical record.

All SAEs and AESIs will be recorded and reported to the sponsor or designee immediately; under no circumstances should this exceed 24 hours, as indicated in [Section 11.4](#). The investigator will submit any updated SAE data to the sponsor within 24 hours of the data being available.

Investigators are not obligated to actively seek information regarding AEs or SAEs after the conclusion of study participation. However, if the investigator learns of any SAE, including a death, at any time after a participant has been discharged from the study, and he/she considers

the event to be reasonably related to the study intervention or study participation, the investigator must promptly notify the sponsor.

#### **8.4.2 Method of Detecting AEs and SAEs**

The method of recording, evaluating, and assessing causality of AEs and SAEs and the procedures for completing and transmitting SAE reports are provided in [Section 11.4](#).

Care will be taken not to introduce bias when detecting AEs and/or SAEs. Open-ended and non-leading verbal questioning of the participant is the preferred method to inquire about AE occurrences.

#### **Clinical Presentation of Adverse Events in Pediatric Population**

Study site staff should instruct the legal guardian(s) on how to report signs and symptoms (e.g. pain) in the individual pediatric participant. The legal guardian(s) will be instructed to report both specific and non-specific symptoms (including vomiting, diarrhea, sleepiness, etc.). These non-specific symptoms may be the only manifestations of some adverse reaction observed. Care should be taken that the clinical presentation of adverse reactions is not misinterpreted as the manifestation of a pre-existing or unrelated condition.

#### **8.4.3 Follow-up of AEs and SAEs**

After the initial AE/SAE report, the investigator is required to proactively follow each participant at subsequent visits/contacts. All SAEs and AESIs (as defined in [Section 8.4.7](#)) will be followed until resolution, stabilization, the event is otherwise explained, or the participant is lost to follow-up (as defined in [Section 7.3](#)). Further information on follow-up procedures is given in [Section 11.4.3](#).

#### **8.4.4 Regulatory Reporting Requirements for SAEs**

- Prompt notification by the investigator to the sponsor of an SAE or AESI is essential so that legal obligations and ethical responsibilities towards the safety of participants and the safety of a study intervention under clinical investigation are met.
- The sponsor has a legal responsibility to notify both the local regulatory authority and other regulatory agencies about the safety of a study intervention under clinical investigation. The sponsor will comply with country-specific regulatory requirements relating to safety reporting to the regulatory authority, Institutional Review Board (IRB), and investigators.
- Investigator safety reports must be prepared for suspected unexpected serious adverse reactions (SUSAR) according to local regulatory requirements and sponsor policy and forwarded to investigators as necessary.
- An investigator who receives an investigator safety report describing an SAE or other specific safety information (e.g. summary or listing of SAEs) from the sponsor will review and then file it along with the Investigator's Brochure and will notify the IRB, if appropriate according to local requirements.

#### **8.4.5 Pregnancy**

- Details of all pregnancies in female participants will be collected after the start of study intervention and until 8 weeks after last dose of study intervention.

- If a pregnancy is reported, the investigator will record pregnancy information on the appropriate form and submit it to the sponsor within 24 hours of learning of the female participant pregnancy.
- While the pregnancy itself is not considered to be an AE or SAE, any pregnancy complication or elective termination of a pregnancy for medical reasons will be reported as an AE or SAE.
- Abnormal pregnancy outcomes (e.g. spontaneous abortion, fetal death, stillbirth, congenital anomalies, ectopic pregnancy) are considered SAEs, and will be reported as such.
- The participant will be followed to determine the outcome of the pregnancy. The investigator will collect follow-up information on the participant and the neonate and the information will be forwarded to the sponsor.
- Any post-study pregnancy-related SAE considered reasonably related to the study intervention by the investigator will be reported to the sponsor as described in [Section 8.4.4](#). While the investigator is not obligated to actively seek this information in former study participants, he/she may learn of an SAE through spontaneous reporting.
- Any female participant who becomes pregnant while participating in the study will discontinue study intervention and be withdrawn from the study after completing the early withdrawal visit.

#### **8.4.6 Disease-Related Events and/or Disease-Related Outcomes Not Qualifying as AEs or SAEs**

The following disease-related event is common in participants with hemophilia A and can be serious/life-threatening:

- Bleeding event

Any bleeding event, regardless if treated or not, occurring during the study will not be documented as an AE, because this is captured in the assessment of effectiveness.

Because these events are typically associated with the disease under study, they will not be reported according to the standard process for expedited reporting of AEs. These events will be recorded in the participant diary.

*NOTE: However, if the bleed fulfills the criterion for an SAE (e.g. results in hospitalization), then the event should be recorded and reported as an SAE (see [Section 11.4.2](#)).*

#### **8.4.7 Events of Special Interest**

Hypersensitivity reactions, including severe allergic reactions (which can progress to anaphylaxis), chest or throat tightness, dizziness, mild hypotension, and nausea, are known and listed adverse drug reactions for FVIII products and have been reported with use of Jivi. Loss of efficacy of the drug product has also been reported in children < 6 years of age and may be associated with the development of antibodies to PEG. Loss of efficacy can present as bleeding and must be confirmed by low recovery or post-infusion FVIII level, and a negative FVIII inhibitor test. A low recovery or no detectable FVIII post-infusion in a participant with a hypersensitivity reaction in the presence of PEG IgM antibodies is considered LoE even in the absence of a bleeding event. All such reported events (hypersensitivity and LoE) occurred early in treatment (within the first 4 EDs).

Hypersensitivity reactions and LoE are defined in this study as AESIs and must be reported within 24 hours of the investigator's awareness. The LoE must be confirmed by an abnormal low recovery after the infusion of Jivi.

In the event of reported LoE of the study intervention, the following is to be done:

1. Schedule a visit within 4 days of the reported event.
2. Obtain 2 pre-infusion blood/plasma samples for FVIII levels and FVIII inhibitor (for local laboratory).
3. Administer BAY 94-9027 (use current prophylaxis dose [IU/kg]).
4. Obtain one post-infusion blood/plasma samples (for local laboratory) for FVIII levels (15-30 minutes post-infusion).

Non-serious hypersensitivity events should not automatically be upgraded by the reporting investigator to serious.

If hypersensitivity reactions occur, immediately discontinue study intervention administration and initiate appropriate treatment. Please refer to the approved prescribing information.

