g If the investigator feels the baseline peak FVIII level at 15-30 minutes or 4-8 hours post-infusion at Visit 2 does not seem to be appropriate for the dose infused, then, if possible, the levels should be repeated at Visit 5 and the results also uploaded to WAPPS-Hemo. For those patients who do not have appropriate FVIII levels at either Visit 2 or Visit 5, the levels should be repeated at Visit 6.

h WAPPS-Hemo data entry should include FVIII levels measured pre-dose, post-infusion, hour 4-8 at Baseline (Day 1) and Month 3 (Visit 5; 72 hours after the last Jivi infusion).

i von Willebrand factor levels should be recorded within 12 months of screening. Please refer to [Section 8.3.4](#) for timing of von Willebrand factor blood draw.

j At Month 3 (72 hours after the previous infusion for all subjects). Post-infusion FVIII levels will be measured for all participants and included in the WAPPS-Hemo analysis.

k Only (S)AEs which are related to protocol-required study procedures will be recorded from the signing of the consent form until the start of study intervention.

l The first Jivi dose will be administered at the clinic at Baseline (Day 1) and may be administered at the clinic at Month 3 (Visit 5) and Month 6 (EOS/Early withdrawal; as long as the infusion does not occur before blood sampling). All other doses will be self-administered at home.

m In case of any infusion-related AE at a site visit, vital signs will be collected.

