### **11.7.3 Visit 3, 4 – (Months 1, 2)**

This visit should take place via telephone.

- Dose regimen adjustment according to score. At Visit 3 for medium risk participants and Visits 3 and 4 for low risk participants
- At home infusion of Jivi
- Concomitant medication review
- AE/SAE/AESI review
- Check of eDiary entries and bleeding history

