### **11.7.4 Visit 5 – (Month 3)**

This in-person visit should take place 72 hours after the last infusion of Jivi.

- Collect information on physical activity level (medium/high [contact sports]; low [non-contact sports]; sedentary)
- Measurement of weight
- Blood sample collection 3 days after previous dose for all participants: FVIII (Jivi) levels for all participants for Web-accessible Population Pharmacokinetic Service-Hemophilia (WAPPS-Hemo) PK analysis. For participants on the 2x/week regimen, collected samples will also serve as a trough level measurement.
- If the PI feels the baseline peak FVIII level at 15-30 minutes or 4-8 hours post-infusion at Visit 2 does not seem to be appropriate for the dose infused, then the levels should be repeated at Visit 5 and the results also uploaded to WAPPS-Hemo. For those patients who do not have appropriate FVIII levels at either Visit 2 or Visit 5, the levels should be repeated at Visit 6.
- Pregnancy test (female participants)
- Infusion of Jivi at study site (not mandatory)
- Concomitant medication review
- AE/SAE review
- Administration and completion of PRO questionnaire (EQ-5D-5L only)
- Return used vials, and dispense remainder of study intervention
- Check of eDiary entries and bleeding history

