### **11.7.5 Visit 6 – (Month 6, End of Study/Early Withdrawal)**

This in-person visit should take place in alignment with the weekly prophylaxis regimen (i.e. as close as possible to the participant's next infusion) as follows: on Day 4 for participants on the 2x/week regimen, on Day 5 for participants on the Q5D regimen, and on Day 7 for participants on less frequent regimens (e.g. Q7D).

The following procedures and assessments will be performed in participants at the EOS visit or at the time of premature termination:

- Concomitant medication review
- AE/SAE/AESI review
- Physical examination including height and weight
- Assessment of joint status
- Collect information on physical activity level (medium/high [contact sports]; low [non-contact sports]; sedentary)
- Blood sample collection **before** administration of study intervention: FVIII (Jivi) trough levels
  - Sample collection on Day 4 for participants on the 2x/week regimen, on Day 5 for participants on the Q5D regimen, and on Day 7 for participants on less frequent regimens (e.g. Q7D)
- Pregnancy test (female participants)
- In-hospital infusion of Jivi
- If the PI feels the baseline peak FVIII level at 15-30 minutes or 4-8 hours post-infusion at Visit 2 does not seem to be appropriate for the dose infused, then the levels should be repeated at Visit 5 and the results also uploaded to WAPPS-Hemo. For those patients who do not have appropriate FVIII levels at either Visit 2 or Visit 5, the levels should be repeated at Visit 6.
- Administration and completion of PROs (Haem-A-QoL or Haemo-QoL, EQ-5D-5L, TSQM, WPAI, and Patient's Global Impression of Change [PGI-C])
- Return used and unused vials
- Check of eDiary entries and bleeding history

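### Step 3 of the LoE work-up and footnote g are not reconciled with the rules for stopping Jivi after hypersensitivity or a low post-infusion FVIII level

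*Protocol*

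**What the plan says.** **The LoE rule.** Protocol Sections 2.3 and 8.3.1 read a low post-infusion FVIII level without a detectable inhibitor as probable anti-PEG loss of effect, and direct a switch to another product. Section 8.3.1 adds that this is an LoE adverse event of special interest (AESI) and refers to 8.4.7. Neither section requires a bleed.

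**Section 8.4.7.** LoE "can present as bleeding and must be confirmed by low recovery or post-infusion FVIII level, and a negative FVIII inhibitor test". A low or undetectable level in a participant with a "hypersensitivity reaction in the presence of PEG IgM antibodies is considered LoE even in the absence of a bleeding event". Once LoE is reported, a four-step list applies: a visit within 4 days, pre-infusion samples for FVIII level and inhibitor, a Jivi infusion at the current prophylaxis dose (step 3), and one post-infusion level. The section closes by telling the investigator to discontinue administration at once if hypersensitivity occurs. On timing it says: "All such reported events (hypersensitivity and LoE) occurred early in treatment (within the first 4 EDs".

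**Footnote g of the Schedule of Activities.** If the investigator feels that a Visit 2 peak "does not seem to be appropriate for the dose infused, then, if possible, the levels should be repeated at Visit 5", with upload to WAPPS-Hemo. Participants who "do not have appropriate FVIII levels at either Visit 2 or Visit 5, the levels should be repeated at Visit 6". Sections 11.7.4 and 11.7.5 carry the same bullet, without the if-possible qualifier. None of the three mentions LoE, an inhibitor test, 8.3.1 or 8.4.7.

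**Visits in between.** For Visits 3 and 4, Section 11.7.3 says: "This visit should take place via telephone". At Visit 5 the on-site dose is optional: "Infusion of Jivi at study site (not mandatory". Visit 6 lists "In-hospital infusion of Jivi".

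**The concern.** A Day 1 recovery sample is the first chance to see loss of effect in an event that has so far appeared within four exposure days. Two instructions could lead a site away from the intended response.

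(a) A participant who has both a hypersensitivity reaction and a low recovery meets the LoE definition, so the work-up list applies on its face. Step 3 has no exception for this participant. A site that follows the list literally would give a further dose to someone who has just reacted.

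(b) A site that sees an implausibly low Day 1 peak finds an instruction in the schedule that fits the situation and names a repeat months later. If it does not also think of 8.3.1, the participant stays on a product that may not be working, and the inhibitor sample in the work-up is not drawn.

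What is at stake is the safety of a small number of participants and the completeness of the LoE count.

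**Working it through.** **Conflict (a), instructions side by side (all in 8.4.7)**

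1. Low recovery plus hypersensitivity plus PEG IgM antibodies is LoE.
2. Reported LoE leads to the four-step list, and step 3 is a Jivi dose.
3. Hypersensitivity leads to discontinuation of administration.

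Items 2 and 3 apply to the same participant and give opposite instructions, with no stated precedence. The conflict does not depend on a PEG result: a reacting participant with a low level and no detectable inhibitor is LoE under 8.3.1, which refers to the same section.

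**Conflict (b), timing**

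Inputs from the protocol: 2x/week dosing at 3- and 4-day intervals in weeks 1 to 4 (Table 4-3), then continued 2x/week, or Q5D from Day 29, or Q5D from Day 29 and Q7D from Day 57; Month 3 visit ±7 days; Month 6 visit +14 days; work-up visit within 4 days.

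Assumptions: Month 3 = Day 92 (Days 85 to 99), Month 6 = Day 183 (Days 183 to 197), Q7D as the less frequent regimen, no missed doses, prophylactic doses only.

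Reproducing the SAP first (Section 4.1.1.4):
- High risk to Day 182: 26 weeks × 2 = 52 doses; 30.4375 × 52 / 182 = 8.6964 per month, as stated.
- Low risk to Day 182: 8 doses (Days 1 to 28) + 6 (Days 29, 34, ..., 54) + 18 (Days 57, 64, ..., 176) = 32; 30.4375 × 32 / 182 = 5.3516 per month, as stated.

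The same counting gives, before Day 92:
- 2x/week: 13 weeks × 2 = 26.
- Q5D: 8 + 13 (Days 29, 34, ..., 89) = 21.
- Q7D: 8 + 6 + 5 (Days 57, 64, 71, 78, 85) = 19.

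Previous infusions, by day of the visit:

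| Regimen | Day 5 | Day 85 | Day 92 | Day 99 | Day 183 | Day 197 |
|---|---|---|---|---|---|---|
| 2x/week | 2 | 24 | 26 | 28 | 52 | 56 |
| Q5D | 2 | 20 | 21 | 22 | 39 | 42 |
| Q7D | 2 | 18 | 19 | 20 | 32 | 34 |

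- Work-up after a Day 1 report: by Day 1 + 4 = Day 5, after doses on Days 1 and 4.
- Delay to the Visit 5 repeat: 85 − 5 = 80 to 99 − 5 = 94 days.
- Delay to the Visit 6 repeat: 183 − 5 = 178 to 197 − 5 = 192 days.
- The first four exposure days are Days 1, 4, 8 and 11, so Visit 5 comes 85 − 11 = 74 to 99 − 11 = 88 days after the fourth.

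Taking Month 3 as Day 91 instead leaves the Visit 5 range at 18 to 28 infusions.

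**The case against.** The strongest reply is that the path already exists. Section 8.3.1 makes a bleed-free low level without detectable inhibitor an AESI, AESIs must be reported within 24 hours, and a reported LoE triggers the 4-day visit with an inhibitor sample. Section 11.7.2 requires a negative inhibitor result before the first dose, so a recent negative is on file when a Day 1 level comes back low. Footnote g is a PK data-quality note covering peaks that look wrong in either direction, and it does not suspend 8.3.1. Extra visits (Section 8) and extra tests (Section 11.3) are allowed, and immediate safety concerns go to the sponsor (Section 8).

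Most of this stands. It rules out three stronger readings that a reader might infer:

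- *That a low level without a bleed is outside the LoE definition or leads to no action.* Section 8.3.1 says otherwise.
- *That the protocol intends re-infusion after a reaction.* The discontinuation rule in 8.4.7 points the other way. What is missing is a statement that it overrides step 3.
- *That the missing PEG assay blocks classification.* The 8.3.1 route needs only a level and an inhibitor result.

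Nor do the documents support requiring a confirmatory dose before every discontinuation. Section 8.4.7 already requires LoE to be confirmed by a low recovery, and a blanket extra dose in suspected LoE would be a preference.

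The reply does not remove the two gaps. Step 3 remains without an exception, and footnote g and its two counterparts remain without a pointer to the safety path. Footnote g was added in Amendment 3, whose change table lists no matching edit to 8.3.1 or 8.4.7.

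**Conclusion.** The point holds as two unreconciled instructions, and its severity is minor. The protocol has the right rule in 8.3.1. Step 3 of 8.4.7 conflicts with the hypersensitivity rule in the same section, and footnote g offers a Month 3 or Month 6 repeat without referring to the rule.

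The counts of 18 to 28 infusions before Visit 5 and 32 to 56 before Visit 6, against 2 before a prompt work-up, are upper bounds. They apply only if a site acts on footnote g and does not act on 2.3 or 8.3.1 in the meantime, and they rest on the visit-day and adherence assumptions above. Few cases should be expected: the reported LoE was primarily in children under 6, this trial enrols from age 12, and the documents give no rate for that age range. The primary endpoint is not affected.

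**What to change.** 1. In 8.4.7, add to step 3 that a participant with a hypersensitivity reaction is not re-infused, and that the recovery already measured plus a new inhibitor sample is used instead.
2. In footnote g, 11.7.4 and 11.7.5, add that a level that is low for the dose is handled under 8.3.1 and 8.4.7, with a visit within 4 days and an inhibitor sample, and that the Visit 5 or Visit 6 PK repeat does not replace this.

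The cost is one sentence in each of four places, with no new assay and no new scheduled visit. Each extra work-up is one unscheduled visit with an inhibitor sample, pre- and post-infusion levels and one on-site dose (no dose after hypersensitivity). If 1 to 3 of the 20 to 25 participants had a low level, which is an assumption, that means 1 to 3 visits. The LoE count may look less favourable. What counts as low remains an investigator judgement unless a cut-off is set in advance.
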